## **2) Potentially effective immunomodulator use**

### **Commencement of a different class of oral, IM, SC, or IV immunomodulator drugs**

(where the subject was not previously taking concomitant immunomodulators of the same class on Day 1 of induction or maintenance), including but not limited to 6-MP, azathioprine, MTX, 6-thioguanine, and prohibited immunomodulators including but not limited to cyclosporine, leflunomide, tacrolimus, thalidomide regardless of dose, for 7 continuous days. The use of an immunomodulator will be considered potentially effective when it is administered for the indication of CD.

## **3) Potentially effective biologic agent use**

**Commencement of a biologic agent** including but not limited to TNF- $\alpha$  antagonists, IL-12/23 antagonists, and vedolizumab (or similar agents), regardless of indication for use and duration.

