**Table 5-1. Prohibited Concomitant Medications**

Drug Class	Agents Disallowed	Prohibited Period
Strong P-gp Inducersa		
Anticonvulsants	Phenobarbital, phenytoin, carbamazepine,	30 days prior to screening through the end of the study
Antimycobacterials	Rifabutin, rifapentine, rifampin	
Herbal/Natural Supplements	St. John's wort, danshen (Salvia Miltiorrhiza)	
Prohibited IBD Medications		
Corticosteroids	Dose equivalent to > 30 mg/day of prednisone	30 days prior to screening through the end of the study
TNF $\alpha$ antagonist	Infliximab, adalimumab, golimumab, certolizumab, or biosimilar agent	8 weeks prior to screening d through the end of the study
Integrin antagonist	Vedolizumab and natalizumab	8 weeks prior to screening d through the end of the study
Interleukin antagonist	Ustekinumab	12 weeks prior to screening d through the end of the study
Other (non-biologic)	Cyclosporine, thalidomide, tacrolimus, leflunomide, and any investigational agent	30 days prior to screening through the end of the study
	Any JAK inhibitor	Any time before and through the end of the study
Investigational biologics	Any investigational biologic agent	8 weeks prior to screening through the end of the study (or at least 5 half lives)
Lymphocyte-depleting therapies	Alemtuzumab, cyclophosphamide, total lymphoid irradiation, rituximab, and any other lymphocyte depleting therapy	Any time before and through the end of the study
Other Prohibited Medications		
Chronic Nonsteroidal Anti-inflammatory Drugs (NSAIDs) b	Aspirin, ibuprofen, naproxen, diclofenac, indomethacin, COX-2 inhibitors	From screening through the end of the study
Other biologics c	Antibody based or other systemic biologics, eg, denosumab, trastuzumab	Requires medical monitor consultation

Abbreviations: COX-2=Cyclooxygenase-2; JAK=Janus Kinase; NSAID=Nonsteroidal Anti-inflammatory Drugs; TNF $\alpha$ =tumor necrosis factor-alpha

- a May decrease study drug exposure and are excluded to avoid potential reduction in study drug activity. PK results indicate that filgotinib is a P-gp substrate, as a single dose of 200 mg itraconazole (a potent P-gp inhibitor) increased filgotinib Cmax by 64% and AUCinf by 45% and had no effect on the major, active metabolite GS-829845.

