- b Occasional use of NSAIDs for transient symptoms and daily use of aspirin up to 162.5 mg for the purpose of cardiovascular prophylaxis are permitted.
- c Other biologics may be allowed with the approval of the medical monitor.
- d Subjects who have an undetectable serum level of a biologic agent since its last dose using a commercially available assay can undergo study screening without the above-mentioned waiting period.

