**Table 6-2. Composite Estimand 1 (Primary Analysis) for Clinical Remission by PRO2**

Attributes	Composite Estimand 1
Treatment	Filgotinib 200 mg, filgotinib 100 mg, or placebo
Population	Full Analysis Set as defined in Section 3.1.2
Subject level endpoint	PRO2 clinical remission status (Yes/No) at Week 10 for Induction Studies and at Week 58 for Maintenance Study If abdominal pain score $\leq 1$ and liquid or very soft stool frequency $\leq 3$ , then the subject will be defined as achieving clinical remission at Week 10 or at Week 58, respectively. If the above remission criterion is not met or the PRO2 (any component) is missing, the subject will be considered as not achieving clinical remission by PRO2.
Handling of missing data due to intercurrent events	Subjects who meet treatment failure criteria (ie, take potentially effective medications other than study treatment as defined in Appendix 6 ) or prematurely discontinue from the study without available assessment result are considered as not achieving clinical remission by PRO2
Population-level summary	Difference in proportions in clinical remission by PRO2, comparing a filgotinib dose group to placebo group

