## Appendix 6. Study Treatment Failure Rules

Study treatment failure rules apply to treatment failure that occurs during the course of the study. Study treatment failure rules will be applied to all efficacy endpoints, unless otherwise specified. All efficacy data will be censored (set to missing) after treatment failure criteria are met, regardless of the observed data. Subjects who do not have sufficient measurements after censoring to determine the dichotomized endpoint(s) will be considered non-responder for corresponding endpoint(s). Study treatment failure rules override other data handling rules.

Subjects who have any of the following events will be considered a study treatment failure after the earliest event through the end of the Induction Study (if the event occurred during Induction) or through the end of the Maintenance Study (if the event occurred during Maintenance), regardless of the actual efficacy data collected. Induction baseline will be referenced when calculating the potentially effective use for Induction Studies, and Maintenance baseline will be referenced when calculating the potentially effective use for Maintenance Study.

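### SAP Appendix 6 rule 3 is not limited to biologics active in Crohn's disease, so read literally it scores a protocol-allowed non-CD biologic as study treatment failure

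*SAP*

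**What the plan says.** **SAP Appendix 6.** Rule 3 is triggered by "Commencement of a biologic agent". It names TNF-α antagonists and continues "IL-12/23 antagonists, and vedolizumab (or similar agents), regardless of indication for use and duration". The named classes are examples only; the list is expressly open.

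The introduction to the appendix sets the consequence: "Study treatment failure rules will be applied to all efficacy endpoints, unless otherwise specified". Efficacy data after the event are discarded whatever was observed. A subject left without enough data is a non-responder, and these rules take precedence over other data handling rules. Failure status lasts to the end of the Induction or the Maintenance Study, whichever the event fell in.

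Rules 1 and 2 are narrower. Rule 1 covers steroids given for CD. Rule 2 says: "The use of an immunomodulator will be considered potentially effective when it is administered for the indication of CD".

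**SAP estimands.** For the co-primary endpoints (Tables 6-2, 6-4 and 6-6), the failure event is described as subjects who "take potentially effective medications other than study treatment as defined in" Appendix 6.

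**Protocol Table 5-1.** Outside the IBD medications, under the heading for other prohibited medications, one row covers "Antibody based or other systemic biologics, eg, denosumab, trastuzumab". Where other rows give a prohibited period, this one says "Requires medical monitor consultation". Footnote c adds: "Other biologics may be allowed with the approval of the medical monitor".

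**The concern.** The composite estimand scores a subject as a failure because another drug may have produced the response. That reasoning covers a TNF antagonist, even one given for another disease. It does not cover a biologic with no action on the bowel.

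Rule 3 as worded makes no such distinction. A subject in observed remission who starts denosumab with approval meets its literal terms. The subject then loses the observed Week 58 remission and endoscopic response for a reason unrelated to CD or to study treatment.

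The wording is also open to two readings. One programmer could follow the operative text and another the heading, and they would score the same subject differently on a co-primary endpoint. A pre-specified failure rule should not leave that choice to be made later.

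**Working it through.** **1. Does the literal rule reach an allowed biologic?**

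| Question | Source | Answer |
|---|---|---|
| What triggers rule 3? | SAP App. 6, rule 3 | Starting a biologic; open list; any indication; any duration |
| Are non-CD biologics excluded? | SAP App. 6, rule 3 | No |
| Is a list of CD biologics available? | SAP App. 2 | Yes, seven entries, without denosumab or trastuzumab; rule 3 does not cite it |
| Can a subject start one within the protocol? | Protocol Table 5-1, footnote c | Yes, conditionally, with approval |
| What happens to later data? | SAP App. 6, introduction | Set to missing; non-responder |
| Do the multiple-imputation analyses relax this? | SAP 6.2.5.1 to 6.2.5.3 | No; failures are set to non-response in every imputed dataset |

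**2. Carry-over from Induction.** SAP 3.1.2 admits a re-randomized subject to the Maintenance Full Analysis Set only if remission by PRO2 or endoscopic response at Week 10 was achieved as the SAP defines it. A start before Week 10 makes the subject a Week 10 non-responder under the SAP, so a subject re-randomized on observed response could drop out of that set.

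**3. Size at Week 58.** Inputs from Protocol 8.9.2: 120 filgotinib 200 mg and 60 placebo subjects, with planned rates of 50% and 20% on each co-primary endpoint. The documents give no rate of non-CD biologic starts. Assume that a share g of each arm starts one, independently of response, with g from 1% to 3%.

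- One misclassified responder: 1/120 = 0.8 points (filgotinib); 1/60 = 1.7 points (placebo).
- Subjects affected: 120 × g = 1.2 to 3.6 (filgotinib); 60 × g = 0.6 to 1.8 (placebo).
- Filgotinib rate lost: 50 × g = 0.5 to 1.5 points.
- Placebo rate lost: 20 × g = 0.2 to 0.6 points.
- Difference lost: (50 − 20) × g = **0.3 to 0.9 points** out of 30.

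If incidence differs by arm, the net change is 50 × g(filgotinib) − 20 × g(placebo). The difference would widen only if placebo incidence exceeded 50/20 = 2.5 times filgotinib incidence.

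**4. Power.** For one endpoint, power = Φ[(|p1 − p2| − 1.96 × SE0)/SE1], with SE0 pooled and SE1 unpooled; co-primary power is the product over the two endpoints, as in the plan.

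- No misclassification: SE0 = √(0.4 × 0.6 × (1/60 + 1/120)) = 0.0775; SE1 = √(0.2 × 0.8/60 + 0.5 × 0.5/120) = 0.0689. Then z = (0.30 − 1.96 × 0.0775)/0.0689 = 2.15, power 0.984, and 0.984² = 96.9%.
- The plan states 94%. A continuity correction gives 95.2%, so neither version matches exactly. Only the change in power is used here.
- With both rates multiplied by (1 − g): 96.6% at 1%, 96.3% at 2%, about 96% at 3%, and 95.2% at 5%.

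For Induction, the same calculation at 1% moves power from 98.1% to 97.9% (CDAI) and from 95.4% to 95.2% (PRO2).

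**The case against.** The strongest objection is that context already limits rule 3. Its heading says potentially effective, every named class is active in CD, and rule 1 explains the term for steroids as drugs that may affect the disease under study. SAP 6.1 labels the resulting non-responders as censored for rescue medication. Denosumab for bone loss fits none of these. This stands as evidence of intent, and a reader should not infer that the sponsor meant every biologic to count as failure. It does not settle the rule, because an open list applied whatever the indication excludes nothing.

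Several stronger readings are tempting, and the documents do not support them:

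- **That rule 3 should be limited to CD indications, like rules 1 and 2.** A CD-active biologic given for another disease can still treat CD, so ignoring indication is right for those agents. The gap concerns which drugs are covered.
- **That the protocol freely permits these biologics.** The row sits in the prohibited-medication table and permission is conditional. Nor does the protocol say how such use should be scored, so no two scoring rules conflict.
- **That the subject fails on every endpoint throughout.** Only data after the start, and within the same study, are lost. A biologic already in use is not caught, since the trigger is a new start.
- **That such starts are common.** Osteopenia/osteoporosis appears in the protocol only as an example of steroid intolerance in eligibility criteria. SAP 3.9 says that the study ran during COVID-19, but neither document mentions therapeutic antibodies for it. Under Protocol 3.5.2, serious infection needing antimicrobial therapy or hospitalization already requires permanent discontinuation of study drug.

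It is also fair to say that the by-treatment counts in SAP 6.1 would show how many subjects were censored for rescue medication, although they do not separate CD from non-CD biologics.

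**Conclusion.** The point holds as a drafting gap in a primary-estimand rule. The operative words of rule 3 reach biologics that cannot be called potentially effective in CD, including ones that the protocol conditionally allows, and the multiple-imputation analyses would not reveal it.

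The effect is small. On an assumed 1 to 3% in each arm, unrelated to response, the planned 30-point Week 58 difference falls by about 0.3 to 0.9 points, and Maintenance power falls by about one percentage point or less. With equal incidence the direction is conservative. A reader might infer a material bias against filgotinib or a threat to the trial's conclusions; nothing in the documents supports either. The 1 to 3% is an assumption with no basis in the documents and serves only to show scale. Severity: minor.

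**What to change.** Before unblinding, amend SAP Appendix 6 rule 3 along these lines:

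> Commencement of any biologic listed in Appendix 2, any similar TNF, integrin or interleukin antagonist, or any investigational biologic for CD, whatever the indication and duration. Other biologics allowed under Protocol Table 5-1, footnote c, are not study treatment failures.

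Have the medical team classify the coded concomitant biologics against this definition, blind to treatment, and file the list before database finalization.

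The cost is a short SAP wording change and a small amount of blinded review. The defensible part of the rule is kept: a CD-active biologic remains a failure even when given for another disease. Which biologics the protocol should allow is a clinical matter that this change leaves alone.

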**Appendix 7. Determining Missing and Virtual Visits due to COVID-19**

This appendix describes the clinical trial site collection of COVID-19 data pertaining to missed/virtual visits and the data processing algorithm used to determine which visits were missing and which visits were virtual.

Data collection

A COVID-19 supplement to the eCRF Completion Guidelines was provided by data management to instruct clinical trial sites with respect to data entry expectations pertaining to scenarios related to the COVID-19 pandemic. If a visit was missed, sites should enter “Visit missed due to COVID-19.” If an in-person visit was conducted virtually, sites should enter “Virtual visit due to COVID-19.”

Determination of Missed and Virtual visits

Natural Language Processing (NLP) was used to search the CRF comment fields to identify instances of “COVID-19” (or synonyms, see [Table 13-7](#)) and “Virtual” (or synonyms, see [Table 13-7](#)). The search terms are maintained in a global lookup table and can be modified to tune the NLP model. For any comments with COVID-19 search terms, assign “Missed visit” or “Virtual visit” as follows:

- i) If COVID-19 terms are identified through NLP and the visit date is missing, then result is “Missed Visit.”
- ii) If COVID-19 and Virtual terms are identified through NLP for a visit, then result is “Virtual Visit”. When there are multiple records for the same subject and the same visit, NLP will be based on multiple records to ensure that only 1 unique visit type (either Missing Visit or Virtual Visit) is assigned for all the records belong to the same visit for a subject.
- iii) Otherwise the visit type is missing.

**Table 13-7. Examples of Search Terms for “COVID-19” and “Virtual” Used to Identify Missed and Virtual Visits**

Search terms for “COVID-19”	Search terms for “Virtual”
COVID19	VIRTUAL
CORONA	TELEMED
CORONAVIRUS	TELEHEALTH
PANDEMIC	TELEPHONE
OUTBREAK	REMOTE
CRISIS	TELEMEDICINE
LOCKDOWN	TELECONSULTATION

---

QUARANTINE SHELTER	TELEPHONICALLY PHONE HOME VISIT ZOOM SKYPE
-----------------------	--------------------------------------------------------

---

## Appendix 8. SAS Programming for Tipping Point Analysis for Binary Endpoint

The following `%tp_binary` macro generates multiple imputed data and a set of the shift parameters that adjust the imputed values will be examined.

```
/*-----*/
/*--- Delta-Adjusting Method for Tipping Point Analysis for Binary Endpoint ---*/
/*---
/*--- Generate imputed data set for specified shift parameters ---*/
/*--- data= input data set ---*/
/*--- smin= min shift parameter for active drug ---*/
/*--- smax= max shift parameter for active drug ---*/
/*--- sinc= increment of the shift parameter for active drug ---*/
/*--- pmin= min shift parameter for placebo drug ---*/
/*--- pmax= max shift parameter for placebo drug ---*/
/*--- pinc= increment of the shift parameter for placebo drug ---*/
/*--- trt= treatment group indicator ---*/
/*--- out= output imputed data set ---*/
/*-----*/

%macro tp_binary( data=, smin=, smax=, sinc=, pmin=, pmax=, pinc=, trt=, out=);
    data &out;
    set _null_;
    run;

/*----- # of shift values -----*/
    %let ncase_pbo = %sysevalf( (&pmax-&pmin)/&pinc, ceil );

    %do pc=0 %to &ncase_pbo;

    %let pj= %sysevalf( &pmin + &pc * &pinc);

        /*----- # of shift values -----*/
        %let ncase= %sysevalf( (&smax-&smin)/&sinc, ceil );

        /*----- Imputed data for each shift -----*/
        %do jc=0 %to &ncase;

            %let sj= %sysevalf( &smin + &jc * &sinc);

                proc mi data=&data seed=14823 nimpute=20 out=outmi;
                    var trt01pn strat1V strat2V strat3V RESP;
                    class trt01pn strat1V strat2V strat3V RESP;
                    monotone logistic (RESP / link=glogit);
                    mnar adjust(RESP (event='1') / adjustobs=(trt01pn="&trt") shift= &sj)
                        adjust(RESP (event='1') / adjustobs=(trt01pn='3') shift= &pj);
                run;

            data outmi;
```

```
        set outmi;  
        Shift_Tr= &sj;  
        Shift_Pbo= &pj;  
        run;  
  
        data &out;  
        set &out outmi;  
        run;  
  
    %end;  
%mend tp_binary;
```

## Appendix 9. MST lists for AEs of Interest

### Herpes Zoster - Galapagos Search Term List MedDRA Version 25.0

TERM_CODE	TERM_NAME	TERM_TYPE
10019974	Herpes zoster	PT
10030865	Ophthalmic herpes zoster	PT
10061208	Herpes zoster infection neurological	PT
10063491	Herpes zoster oticus	PT
10065038	Herpes zoster disseminated	PT
10072210	Genital herpes zoster	PT
10074241	Varicella zoster gastritis	PT
10074243	Varicella zoster oesophagitis	PT
10074245	Herpes zoster pharyngitis	PT
10074248	Herpes zoster meningoencephalitis	PT
10074251	Herpes zoster meningomyelitis	PT
10074253	Herpes zoster necrotising retinopathy	PT
10074254	Varicella zoster pneumonia	PT
10074259	Herpes zoster meningitis	PT
10074297	Herpes zoster cutaneous disseminated	PT
10074298	Varicella zoster sepsis	PT
10075611	Varicella zoster virus infection	PT
10076667	Disseminated varicella zoster vaccine virus infection	PT
10079327	Herpes zoster meningoradiculitis	PT
10080516	Herpes zoster reactivation	PT
10082717	Herpetic radiculopathy	PT
10084396	Disseminated varicella zoster virus infection	PT
10086594	Oral herpes zoster	PT
10086746	Varicella encephalitis	PT
10086747	Varicella meningitis	PT

GLPG0634-CL-MACE, 20DEC22:15:49

**Malignancies, Excluding Nonmelanoma Skin Cancers - Galapagos Search Term List**

**MedDRA Version 25.0**

TERM_CODE	TERM_NAME	TERM_TYPE
10000583	Acral lentiginous melanoma	PT
10000585	Acral lentiginous melanoma stage I	PT
10000586	Acral lentiginous melanoma stage II	PT
10000587	Acral lentiginous melanoma stage III	PT
10000588	Acral lentiginous melanoma stage IV	PT
10000739	Acute erythroid leukaemia	PT
10000830	Acute leukaemia	PT
10000846	Acute lymphocytic leukaemia	PT
10000847	Acute lymphocytic leukaemia (in remission)	PT
10000860	Acute megakaryocytic leukaemia	PT
10000871	Acute monocytic leukaemia	PT
10000872	Acute monocytic leukaemia (in remission)	PT
10000880	Acute myeloid leukaemia	PT
10000881	Acute myeloid leukaemia (in remission)	PT
10000890	Acute myelomonocytic leukaemia	PT
10001019	Acute promyelocytic leukaemia	PT
10001141	Adenocarcinoma	PT
10001150	Adenocarcinoma gastric	PT
10001167	Adenocarcinoma of colon	PT
10001197	Adenocarcinoma of the cervix	PT
10001244	Adenosquamous carcinoma of the cervix	PT
10001245	Adenosquamous cell lung cancer	PT
10001247	Adenosquamous cell lung cancer recurrent	PT
10001248	Adenosquamous cell lung cancer stage 0	PT
10001249	Adenosquamous cell lung cancer stage I	PT
10001250	Adenosquamous cell lung cancer stage II	PT
10001251	Adenosquamous cell lung cancer stage III	PT
10001254	Adenosquamous cell lung cancer stage IV	PT
10001388	Adrenocortical carcinoma	PT
10001413	Adult T-cell lymphoma/leukaemia	PT
10001416	Adult T-cell lymphoma/leukaemia recurrent	PT
10001417	Adult T-cell lymphoma/leukaemia refractory	PT
10001418	Adult T-cell lymphoma/leukaemia stage I	PT
10001419	Adult T-cell lymphoma/leukaemia stage II	PT
10001420	Adult T-cell lymphoma/leukaemia stage III	PT

GLPG0634-CL-MACE, 20DEC22:15:49

**Malignancies, Excluding Nonmelanoma Skin Cancers - Galapagos Search Term List**

**MedDRA Version 25.0**

TERM_CODE	TERM_NAME	TERM_TYPE
10001421	Adult T-cell lymphoma/leukaemia stage IV	PT
10001433	Aesthesioneuroblastoma	PT
10001660	Aleukaemic leukaemia	PT
10001882	Alveolar soft part sarcoma	PT
10001884	Alveolar soft part sarcoma metastatic	PT
10001887	Alveolar soft part sarcoma recurrent	PT
10002133	Anal cancer recurrent	PT
10002134	Anal cancer stage 0	PT
10002135	Anal cancer stage I	PT
10002136	Anal cancer stage II	PT
10002137	Anal cancer stage III	PT
10002138	Anal cancer stage IV	PT
10002224	Anaplastic astrocytoma	PT
10002227	Anaplastic large cell lymphoma T- and null-cell types	PT
10002229	Anaplastic large cell lymphoma T- and null-cell types recurrent	PT
10002230	Anaplastic large cell lymphoma T- and null-cell types refractory	PT
10002231	Anaplastic large cell lymphoma T- and null-cell types stage I	PT
10002232	Anaplastic large cell lymphoma T- and null-cell types stage II	PT
10002233	Anaplastic large cell lymphoma T- and null-cell types stage III	PT
10002234	Anaplastic large cell lymphoma T- and null-cell types stage IV	PT
10002240	Anaplastic thyroid cancer	PT
10002411	Angiocentric lymphoma	PT
10002414	Angiocentric lymphoma recurrent	PT
10002415	Angiocentric lymphoma refractory	PT
10002416	Angiocentric lymphoma stage I	PT
10002417	Angiocentric lymphoma stage II	PT
10002418	Angiocentric lymphoma stage III	PT
10002419	Angiocentric lymphoma stage IV	PT
10002449	Angioimmunoblastic T-cell lymphoma	PT
10002452	Angioimmunoblastic T-cell lymphoma recurrent	PT
10002453	Angioimmunoblastic T-cell lymphoma refractory	PT
10002454	Angioimmunoblastic T-cell lymphoma stage I	PT
10002455	Angioimmunoblastic T-cell lymphoma stage II	PT
10002456	Angioimmunoblastic T-cell lymphoma stage III	PT
10002457	Angioimmunoblastic T-cell lymphoma stage IV	PT

GLPG0634-CL-MACE, 20DEC22:15:49

